10.9 Participant Identification Centres

Participant Identification Centres (PICs) will not be used in this study. The identification of participants will be done by the recruiting centres only.

11 SUB-STUDIES/TRANSLATIONAL STUDIES/MECHANISTIC STUDIES

The following mechanistic studies will seek to:

- 1. Identify the immune pathways in skin and SOT rejection and compare these to known mechanisms;
- 2. Characterise the mechanisms by which simultaneous transplant of skin and SOT modulates the immune system. We will explore the role of passenger leucocytes, suppressor Tcells, immune diversion or paralysis, and lymphocytotoxic antibodies;
- 3. Examine the relative proportions of T-cells of both donor and recipient origin and the role of skin homing of T-reg cells in preventing rejection;
- 4. Establish whether serum cell-free DNA levels correlates with detected rejection;
- 5. Determine the role of cutaneous and lung microbiome on the immunological response.

Most studies have used samples collected when rejection and organ injury are already well-established. We have a unique collection of very early-phase rejection samples from intestinal and pancreas transplants. We will collect samples from lung transplants in this study to analyse and compare to non-rejection samples.

Within the Transplant Research Immunology Group, at the University of Oxford we will perform an un-biased high throughput assay to determine DNA, RNA and protein biomarkers related to the systemic and local alloresponse to the transplants, as well as targeted analysis of changes in known markers such as those involved in CXCL9, CXCL10, & IL-1.

Firstly, to characterise the local response in skin and lung transplant, NanoString nCounter gene expression analysis for mRNA quantification will be performed. We will use the human immunology panel v2, which measures 579 genes relating to the core pathways and processes of the immune system, with 15 internal reference genes included for normalization, and compare non rejection to rejection episodes.

Secondly, selected tissue biopsies will be further analysed using Digital Spatial Profiling. This will demonstrate exactly where within the tissue cells and genes of interest are being expressed.

Thirdly, SSF and SOT rejection biopsies will be analysed by expert transplant histopathologists. They will use quantitative multiplex immune-profiling to focus on those factors involved in rejection and tolerance, including CD8⁺T cells, CD4⁺T conventional cells (CD4⁺FoxP3⁻), Tregs (CD4⁺FoxP3⁺), CD68+ and PD-L1 using fluorescent antibodies against CD4, CD8, FoxP3 and nuclear stain to determine spatial distribution of immune infiltrates. Finally, the molecular profile of single cells within regions of interest will be determined using a panel of 40 immune-related barcoded antibodies or up to 800 RNA probes or by total single cell gene analysis. 16S ribosomal RNA gene sequencing will identify the microbiome changes over time and ACR.

Whenever a lung biopsy is taken as part of standard clinical care, an additional skin biopsy will also be taken at the same time for participants that have received a SSF transplant. In addition to routine follow-up and examination, surveillance biopsies of the SSF will be performed at routine appointments after transplantation at 3, 6 and 12 months.

12 PARTICIPANT ELIGIBILITY CRITERIA

12.1 Timing of eligibility assessment

Eligibility will be confirmed following Stage 1 consent, however once the participant has been matched with a suitable donor and confirmed their consent for study participation (Stage 2 consent) a final check of eligibility will be made prior to randomisation.

Participant eligibility will be confirmed by a suitably qualified and experienced individual who has been delegated to do so by the Principal Investigator. Eligibility will be assessed upon initial entry into the study and again as part of the Stage 2 consent process once the participant has been matched with a donor prior to randomisation.

12.2 Overall description of trial participants

The SENTINEL study will recruit adults aged 18 years and over awaiting lung transplantation, including single, bilateral or heart-lung transplantation.

Written informed consent must be obtained before any study specific procedures are performed. The Investigator will determine patient eligibility based on the following criteria.

12.3 Inclusion Criteria for entry into the main trial

A patient will be eligible for inclusion in this study if all of the following criteria apply.

- 1. Intended recipient of a lung transplant
- 2. Aged 18 years or over
- 3. Willing and able to give informed consent

12.4 Exclusion Criteria for entry into the main trial

A patient will not be eligible for the trial if **ANY** of the following apply:

- 1. Any significant disease or disorder which, in the opinion of the Investigator, may either put the participants at risk because of participation in the study, or may influence the result of the trial, or the participant's ability to comply with trial procedures
- 2. Severe peripheral vascular disease with no vessels available for inset of the skin flap

12.5 Rationale for inclusion and exclusion criteria

Patients must already be on the lung transplant waiting list, having passed the rigorous process to establish the necessity for a lung transplant independently from the study.

Patients under the age of 18 are excluded, as they are perceived not to fully comprehend the risks and benefits of participating in the study.

Patients have to be able to give informed consent. Some patients may be intubated and ventilated and therefore unable to communicate with the trial staff and therefore will be deemed ineligible.

Patients with severe peripheral vascular disease in the recipient upper limb may be ruled ineligible as the risk of being unable to perform the skin flap transplant may be deemed too high. However, if an alternative healthier site for transplant can be agreed upon then they may still be eligible.

If, on donation the donor's relatives agree to lung donation only, then the recipient will be ineligible to be randomised in the study as the skin flap option is absent. In this case the recipient will proceed with lung transplantation alone outside of the study and no further data collection will occur.

12.6 Protocol waivers to entry criteria

Protocol adherence is a fundamental part of the conduct of a research study. There will be no waivers regarding eligibility i.e. each participant must satisfy all the eligibility criteria. Changes to the approved inclusion and exclusion may only be made by a substantial amendment to the protocol.

Before enrolling a patient onto the study, the Principal Investigator or designee will confirm eligibility. If unsure whether the patient satisfies all the entry criteria and to clarify matters

of clinical discretion, investigators must contact the Trial Office, who will contact the Chief Investigator or designated clinicians as necessary. If in any doubt, the Chief Investigator must be consulted before enrolling the patient. Details of the query and outcome of the decision must be documented in the TMF.

12.7 Clinical queries and protocol clarifications

Every care has been taken in drafting this protocol. Contact the SENTINEL Trial Office for clarification if any instructions seem ambiguous, contradictory or impractical. Clinical queries must also be directed to the Trial Office. All clinical queries and clarification requests will be logged, assessed and a written response provided. Minor administrative corrections or clarifications will be communicated to all trial investigators for information as necessary. For urgent safety measures or changes that require protocol amendment see Urgent safety measures section below.

13 SCREENING AND RECRUITMENT

13.1 Participant Identification

Participants will be recruited from all five lung transplant centres in England. The following methods will be used to identify potentially eligible participants:

- Identification during routine clinic visits
- Searching of the lung transplant waiting list by the usual care team to identify individuals that may be eligible and are awaiting lung transplantation

Organs may be retrieved from donors at any hospital in England and Wales.

13.2 Identification of participants during routine clinic visits

Patients awaiting lung transplantation will undergo regular routine monitoring whilst on the transplant register. Potentially eligible patients identified during routine clinic visits will be provided with a Patient Information Sheet (PIS) by a member of their usual care team (who may also be a member of the research team) and asked to consider the study. Where their usual care clinician is not a member of the research team, potential participants will be asked for permission for the research team to contact them regarding the study. If permission is given, it should be recorded in their clinical notes. A member of the research team will make contact with them in a clinic visit or arrange a telephone or video call. Alternatively, patients may be given the participant information sheet and asked to call the number on it if they wish to find out more about the study.

13.3 Identification of participants via clinic records/hospital database

Potentially eligible patients may also be identified by searching clinic records/hospital databases by the local care team. Any patients who are thought to fulfil the inclusion/exclusion criteria may be sent a letter of invitation and patient information sheet by the local care team. A reply slip and postage paid envelope will be included, enabling potential participants to indicate how they would prefer to be contacted further about taking part in the study.

13.4 Use of screening logs

A screening log will be kept of all patients who are approached about the study. It will log the number of patients who decline further information about the study and their reasons. It will also log those who do not meet the inclusion criteria for the study, and record the reasons for exclusion. In addition, the number of eligible patients, and whether they

SENTINEL_Protocol_V1.1_27Apr2023.docx IRAS number: 318347 REC Reference: 23/LO/0248

consent to the study will be recorded. It will also provide information on participants who decline or later withdraw consent and their reasons for doing so.

13.5 Pre-study screening tests or investigations

There are no study-specific screening procedures.

14 INFORMED CONSENT

14.1 Consent Procedure – Trial Participant (transplant recipient)

Prior to any study related procedures or data being collected the patient must personally sign and date the latest approved version of the Informed Consent Form (ICF).

Patients awaiting lung transplantation may remain on the lung transplant register for some time, therefore consent for study participation will be taken in two stages:

Stage 1 consent: Initial consent for inclusion in the study will be taken whilst the

participant is on the lung transplant register and awaiting

transplantation

Stage 2 consent: Confirmation of final and full informed consent will be taken once the

participant has been matched with a suitable donor (where a

donation offer of both lungs and skin has been made)

Study participants will be matched with a suitable lung transplant donor as soon as they become available in accordance with NHSBT procedures. They may therefore be matched to a lung transplant donor where an offer of skin flap donation has not been made. In this situation the participant will not proceed to randomisation in the study and lung only transplantation will take place.

14.2 Timing of consent

Due to the emergency, unplanned nature of transplant procedures and the wish to have unhurried timely discussion with adequate period for digestion of the information, reflection and exchange of questions and answers; discussion about the study will be undertaken whilst patients are on the transplant waiting list. If patients agree to participate in the study consent will be taken and recorded whilst they are on the transplant waiting list (Stage 1 consent). In the event they are later matched with a donor and selected for transplantation, then consent will be confirmed prior to the procedure (Stage 2 consent).

14.3 Stage 1 consent (participant/ recipient)

A member of the responsible clinical team will briefly highlight the study to the patient and introduce a member of the local research team. If it is not possible for research staff to approach patients at the first point of contact, the patient can give their verbal permission for their details to be passed to the local research team who will make contact with the patient by their preferred method and in accordance with the local site policy. Potential participants will be given a current, approved version of the patient information sheet. They will also receive clear verbal information about the study from a member of the local research team. This will detail the nature of the study; the implications and constraints of the protocol; the known side effects and any risks involved in taking part. It will be

explained that they will be free to withdraw from the study at any time, for any reason, without prejudice to future care, and with no obligation to give a reason for withdrawal.

Due to the nature of the intervention, the timing of transplantation and the requirement for a dedicated transplant retrieval team, potential participants will also be advised that if they do join the study, it may not always be possible for them to receive an SSF or one may not always be available for transplantation. In this instance, the patient will not be able to take part in the study, but they will receive a lung transplant as planned and current NHS standard practice.

Patients will be given as much time as they wish to consider the information, and have the opportunity to question the Investigator, their GP or other independent parties to decide whether they will participate in the study. It will be clearly stated that the participant is free to withdraw from the study at any time, for any reason without prejudice to future care, without affecting their legal rights, and with no obligation to give the reason for withdrawal.

The person obtaining consent must be suitably qualified, experienced and have been authorised to do so by the site's Principal Investigator. They are responsible for ensuring that the consent procedures comply with current applicable GCP Regulatory and ethical requirements. Informed consent discussions and outcomes must be well documented in the participants medical record.

14.4 Completion of the informed consent form (Stage 1)

The informed consent form (ICF) will usually be offered to participants in clinic as an electronic form on a tablet device (with the consent form being filled in directly on the study database, REDCap), however paper consent forms will also be made available for use in situations where electronic consent is not possible or suitable. Where it is not possible for a consent form to be completed in clinic, remote electronic consent may also be used.

A copy of the fully signed consent form will be given to the participant; where electronic consent is used and the participant has an email address they are willing to provide, an electronic version of the signed ICF will be automatically emailed to them. If the participant does not have/does not provide an email address the local team will be able to print a copy of the signed ICF and provide this to the participant. Consent forms will be e-mailed securely to the participant. The original signed consent form (paper consent only, for electronic consent this will be downloaded from the study database) should be placed in the Investigator Site File and a copy in the participant's medical record.

Remote eConsent (if required) will be obtained in accordance with OCTRU's standard operating procedures for obtaining consent. Where remote consent will be used, potential participants will be asked to provide an e-mail address for receiving consent documents, prior to obtaining written informed consent. Potential participants will receive a unique link via e-mail to an electronic consent form which may then be completed remotely. Once completed, this form will be sent via e-mail to the participant as a PDF document. A member of the local site research team will be required to countersign all consent forms completed remotely, in the same way as for paper forms and verify the identity of the participant.

14.5 Stage 2 consent (participant/recipient)

If the intended recipient has given Stage 1 consent to be included in the study, they will be approached by the recipient point of contact at the recipient centre at the time of offer of organs. They will be asked to give confirmation of full informed consent (Stage 2) for the study in order to proceed. This will be on or close to the day of transplantation. Due to the need to randomise participants in a timely manner to allow sufficient time for the dedicated skin flap retrieval team to travel to the donor site (for those participants randomised to this arm of the study), it may be necessary to discuss confirmation of consent over the telephone prior to the participants arrival at the transplant centre. This will permit randomisation and skin flap retrieval to proceed. Where telephone consent is taken, written consent will be sought as soon as it is practically possible.

Patients that give Stage 2 consent will be randomised to either proceed with lung and skin flap transplant or lung transplant alone when a set of lungs and skin flap are donated and matched by NHSBT.

14.6 Patients lacking capacity to consent

Patients that do not have capacity to consent to study participation will not be eligible to enter the study.

14.7 Consent Procedure – transplant (lung and skin flap) donor's families

[figure not shown]
Note: This is as per standard UK practice – the process is not affected by the study nor details recorded by the study team.

Consent for donation of lung will be taken in accordance with usual NHS blood and transplant service (NHSBT) policies and guidelines. Current practice in the UK is for the NHSBT Specialist Nurses (SNs), as part of discussions if the offer of donation is made, to discuss organ donation with families and seek consent for donation using a standard NHSBT consent form. The Specialist Nurses will receive comprehensive study-specific training to an SOP which will be available for them to follow electronically when out on call. Training records will be recorded and kept by NHSBT. The SOP and training will include any information that needs to be given to the family and there will also be a step-by-step process for the SNs to follow to facilitate the skin flap donation process including giving the SENTINEL relative information sheet for the donors relatives to read. Donor families will be approached for consent for donation of the forearm SSF as a VCA which will be recorded as an organ for transplantation on the standard NHSBT consent form.

Note: All offers of donation will be recorded on NHSBT consent forms/paperwork – donor families will not complete any SENTINEL documentation.

14.8 Transplant pathway following consent

Patients awaiting lung transplantation may be on the waiting list for a transplant for some time. Following initial agreement to join the study (Stage 1 consent), numerous factors will determine whether a participant will proceed in the study. The flow chart overleaf provides an overview of the participant pathway following consent to the point of transplantation.

14.9 GP notification

Permission from the participant will also be obtained to inform their GP of their inclusion in the study. An approved GP letter will be sent by the research team to the participant's GP informing them of their participation in the trial post-transplantation.

14.10 Re-consenting

Should there be any subsequent amendment to the final protocol, which might affect a participant's participation in the study, continuing consent will be obtained using an amended consent form which will be signed by the participant.

14.11 Participants who lose capacity during the study

Patients that initially consented to the study (Stage 1 consent) but have lost capacity and are unable to provide confirmation of consent (Stage 2 consent) immediately prior to transplantation will not be eligible to be randomised and will be excluded from being able to be randomised.

If any participants permanently lose capacity during the course of the study after they have consented, randomised and been transplanted (this will be decided by their clinical care team, then we will continue to use data already collected and no further data will be collected.

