9.2 Primary objective and outcome measure

Objective	Outcome measure	Time point(s) of evaluation of this outcome measure (if applicable)	Data required	Source data (including location)
To assess the efficacy of the sentinel skin flap (SSF) at reducing rates of acute lung rejection by 12 months post-transplantation	in the first 12 months, diagnosed	first rejection event in	Date of randomisation; date of first diagnosed lung rejection; date of death (if prior to diagnosis of lung rejection); date of withdrawal (if prior to diagnosis of lung rejection).	Participant's medical notes (clinical diagnosis); Histology report (biopsy diagnosis)

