17.7 Withdrawal of participant by the clinician

Withdrawal from the study or parts of the study may come from clinicians if they believe the participant needs to be withdrawn. Under these circumstances, the site needs to document the reason for the clinician's withdrawal of the individual in the participant's medical notes. The site should notify the SENTINEL study office, which will allow them to mark all future CRFs as not applicable. However, under these conditions, investigators are still responsible to follow up any SAEs, and continue to report the SAE to resolution in the CRF and to the study centre.

The type of withdrawal will be collected on the CRF.

Data and samples collected up to the point of withdrawal will be used in the study analysis.

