24.9 Inclusion in analysis

The principle of intention-to treat (ITT), as far as practically possible will be the main strategy for the primary outcome and all secondary outcomes (except for Secondary Outcome 2d). ITT will analyse all randomised and transplanted patients, in the group to which they were allocated and for whom the outcomes of interest have been

observed/measured. To check the robustness of analysis under ITT, a secondary sensitivity per-protocol analysis, which will mirror the ITT population but exclude participates defined with a major protocol deviation, will be conducted. Secondary outcome 2d (safety events) will be analysed according to the safety population, which will include all participants who receive a transplant, where groups are defined according to whether or not they received a skin transplant.

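### Sections 14.11 and 17.7 stop outcome capture in transplanted participants who have not withdrawn consent, so first rejection, graft loss and death may be lost informatively, in an unknown direction

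*Protocol*

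**What the plan says.** **Loss of capacity.** Protocol 14.11 covers participants who permanently lose capacity after consent, randomisation and transplant. The rule is "then we will continue to use data already collected and no further data will be collected". No exception is stated, not even for SAEs.

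**Withdrawal by a clinician.** Protocol 17.7 opens: "Withdrawal from the study or parts of the study may come from clinicians if they believe the participant needs to be withdrawn". No criteria follow. The consequence is: "The site should notify the SENTINEL study office, which will allow them to mark all future CRFs as not applicable". The one stated exception is that "investigators are still responsible to follow up any SAEs".

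**Withdrawal of consent** is a separate matter. Section 17.6 bars later data, routine-care data included, only when the participant withdraws completely, and it lists graded partial options.

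**Analysis.** The primary-outcome data in 9.2 include "date of withdrawal (if prior to diagnosis of lung rejection"). Under 24.9, "ITT will analyse all randomised and transplanted patients, in the group to which they were allocated", provided the outcome was observed. Sections 24.4 and 24.14 specify complete cases, no imputation, and censoring at the last available measure.

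**The concern.** In neither rule has the participant refused follow-up, yet recording stops. The information still exists. Section 9.2 takes the primary outcome from medical notes and histology reports, and 10.4 says local teams collect lung transplant outcomes for NHSBT in any case.

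Censoring at withdrawal treats the later risk of those who leave as equal to that of those who stay. That is doubtful here, because severe illness after transplant can plausibly cause both loss of capacity and a poor outcome. Clinician withdrawal is decided by site staff who know the allocation (15.7). First lung rejection is at stake for the primary analysis. Graft loss and death are at stake for secondary outcome 2b and for the composite of rejection-free survival in 24.8. The 15% allowance in 24.2 protects precision and does nothing about informative loss.

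**Working it through.** **1. Does the SAE exception in 17.7 recover the outcomes?**
- Section 20 treats rejection as a study outcome, recorded on the complications CRFs and kept off the SAE route.
- Section 19.3 has sites report only SAEs judged related to study procedures, so an unrelated death is not reported.
- Section 19.4 lists lung failure and explant as complications that normally stay off the SAE form.
- Section 25.4 puts all trial data on the CRF, and the later CRFs are the ones marked not applicable.

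The exception therefore captures neither rejection nor unrelated death, and normally not graft loss.

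**2. The plan's sample size.** Inputs from 24.2: 80% versus 53.33%, two-sided 5%, 90% power, 15% loss or death. With the pooled-variance formula and mean rate 0.6667:

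n = [1.96 × √(2 × 0.6667 × 0.3333) + 1.2816 × √(0.8 × 0.2 + 0.5333 × 0.4667)]² / 0.2667²
= (1.307 + 0.819)² / 0.0711 = 63.6, so 64 per arm and 128 in all.

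64 / 0.85 = 75.3, so 76 per arm and 152 in all. The stated figures reproduce, and the point below does not change them.

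**3. Size of a possible shift.** The protocol gives no rate for either kind of withdrawal, so what follows is assumption: k participants of 76 are lost before any event, every one would have rejected, and they leave the denominator as a complete-case analysis requires. The observed rate is then (76p − k) / (76 − k).

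| Participants lost | Flap arm observed | Control arm observed | Risk difference | Shift from 26.67 |
|---|---|---|---|---|
| 2, flap only | (40.53 − 2)/74 = 52.07% | 80% | 27.93 | +1.3 |
| 5, flap only | (40.53 − 5)/71 = 50.05% | 80% | 29.95 | +3.3 |
| 2, control only | 53.33% | (60.80 − 2)/74 = 79.46% | 26.13 | −0.5 |
| 5, control only | 53.33% | (60.80 − 5)/71 = 78.59% | 25.26 | −1.4 |
| 5 in each arm | 50.05% | 78.59% | 28.54 | +1.9 |

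The planned Cox model would also use the time before censoring, so these figures are a guide to scale and not a forecast.

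**4. If there is truly no effect** (80% in both arms) and losses fall only in the flap arm on the same worst-case terms, 5% lost gives a spurious difference of 1.1 points and a two-sided type I error of about 5.3%. At 10% lost the figures are 2.2 points and 6.3%.

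**The case against.** The case on the other side is substantial, and much of it stands.

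- **A reader might infer that any clinician withdrawal ends all capture.** Section 17.7 provides for partial withdrawal, records the type, and does not repeat the ban on routine-care data in 17.6. The defect is narrower: the instruction to "mark all future CRFs as not applicable" is not tied to full withdrawal.
- **A reader might infer that the error favours the flap.** The documents do not support that. The capacity rule is the same in both arms, and nothing suggests that the flap affects capacity. Flap complications are met by flap removal (16.12), and a participant's request for removal is its own partial withdrawal type (17.6). The withdrawal option in 16.5 concerns where the flap can be sited, not withdrawal after transplant.
- **Persistent lung rejection cannot be lost from the primary analysis this way.** Under 24.5 the first rejection is the event and is already counted.
- **A reader might read 2/76 to 5/76 (2.6% to 6.6%) as the bias.** That would keep the lost participants in the denominator as non-events, whereas the plan removes or censors them.
- **A reader might see the entry criterion "Willing and able to give informed consent" as being re-applied after randomisation.** No one is removed from their allocated group for losing capacity: earlier data are kept, and the trigger is permanent loss only.
- **The capacity rule is a consent choice under ethics review, and minimal attrition is expected (24.14).** Both are fair points. They limit the size of the problem and constrain the remedy.

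One reply does not stand, namely that the SAP can deal with it. An SAP can describe how missing data are handled, but it cannot recover outcomes that the protocol says not to collect.

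**Conclusion.** The concern holds in a limited form. Followed as written, 14.11 stops all later data for a transplanted participant who permanently loses capacity, and 17.7 can do nearly the same on a clinician's judgement, in neither case because consent was withdrawn. First rejection, graft loss and death may then be lost for reasons linked to prognosis, under an analysis that assumes otherwise.

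The direction is unknown and the number affected is probably small. The 1.3 to 3.3 point shift rests on three assumptions that the protocol does not support or refute: losses in the flap arm only, all before a first event, and all in participants who would have rejected. Losses in the control arm would offset it in part or reverse it. Even at the top of that range, the shift is small beside the 26.67-point target. This is a worthwhile and inexpensive improvement, not a threat to the design.

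**What to change.** **Section 17.7.** State that clinician withdrawal stops only study-specific procedures (samples, questionnaires, study visits). State that lung rejection, graft status, complications and death continue to be recorded from medical notes to 12 months unless the participant withdraws consent for data. Reword the CRF instruction to match.

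**Section 14.11.** Stop samples and questionnaires when capacity is permanently lost. At Stage 1 and Stage 2 consent, while the participant has capacity, seek advance agreement that routine-record outcomes and death may be collected to 12 months if capacity is later lost. This is subject to REC approval.

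**Reporting.** Give the number and timing of both kinds of withdrawal by arm.

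**Cost.** An REC amendment, revised consent wording and a little extra extraction from notes. The sample size stays at 152.
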